4.1.1 Inclusion Criteria

- 1. Male or female subjects, aged 8-12 years (inclusive) at the time of screening.
- 2. Diagnosis of ADHD according to the *Diagnostic and Statistical Manual of Mental Disorders-5* (DSM-5) confirmed by MINI-KID.
- 3. R-MOAS score of \geq 20 at screening.
- 4. CGI-S score ≥4 at screening.
- 5. Vitiello Aggression Scale score from -2 to -5 at screening.
- 6. Treatment with FDA-approved optimized ADHD medication (i.e., psychostimulants) at an FDA-approved dose for at least 1 month prior to screening, and willing to maintain that dose throughout the Treatment phase.
- 7. Free of antipsychotic medication for at least 2 weeks prior to the treatment.
- 8. Medically healthy and with clinically normal laboratory profiles, vital signs, and ECGs.
- 9. Weight of at least 20 kg.
- 10. Able and willing to swallow tablets whole and not chewed, cut or crushed.
- 11. Written Informed Consent obtained from the subject's parent or legal representative, and written Informed Assent obtained from the subject, if appropriate.

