6.3.9.4 Columbia-Suicide Severity Rating Scale (C-SSRS) (Section 12.6)

The C-SSRS is a questionnaire that prospectively assesses suicidal ideation and behavior using a semi-structured interview to probe patient responses (Posner et al., 2011). The C-SSRS versions applicable to the current study are the Baseline version and the Since Last Visit version (Visit 1, Visit 4 and Visit 6).

The Baseline version of the scale assesses lifetime suicidal ideation and behavior. This version is suitable as part of a subject's first interview and will be used at Visit 1 to identify volunteers who must not participate in the trial due to their suicidal tendencies.

The Since Last Visit version of the scale assesses any suicidal thoughts or behaviors the subjects may have had since the last administration of the C-SSRS. This version will be used for the other study visits.

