12.6 Columbia-Suicide Severity Rating Scale (C-SSRS)

12.6.1 C-SSRS, Children's Baseline/Screening

COLUMBIA-SUICIDE SEVERITY RATING SCALE (C-SSRS)

Children's Baseline/Screening

Version 6/23/10

Posner, K.; Brent, D.; Lucas, C.; Gould, M.; Stanley, B.; Brown, G.; Fisher, P.; Zelazny, J.; Burke, A.; Oquendo, M.; Mann, J.

Disclaimer:

This scale is intended to be used by individuals who have received training in its administration. The questions contained in the Columbia-Suicide Severity Rating Scale are suggested probes. Ultimately, the determination of the presence of suicidal ideation or behavior depends on the judgment of the individual administering the scale.

Definitions of behavioral suicidal events in this scale are based on those used in The Columbia Suicide History Form, developed by [name] and [name], Conte Center for the Neuroscience of Mental Disorders (CCNMD), New York State Psychiatric Institute, [name]. (Oquendo M. A., Halberstam B. & Mann J. J., Risk factors for suicidal behavior: utility and limitations of research instruments. In M.B. First [Ed.] Standardized Evaluation in Clinical Practice, pp. 103-130, 2003.)

For reprints of the C-SSRS contact [name]., New York State Psychiatric Institute, [name]; inquiries and training requirements contact [contact]

© 2008 The Research Foundation for Mental Hygiene, Inc.

SUICIDAL IDEATION				
Ask questions 1 and 2. If both are negative, proceed to "Suicidal Behavior" section. If the answer to question 2 is "yes", ask questions 3, 4 and 5. If the answer to question 1 and/or 2 is "yes", complete "Intensity of Ideation" section below.		time	Past 6 Months	
1. Wish to be Dead Subject endorses thoughts about a wish to be dead or not alive anymore, or wish to fall asleep and not wake up. Have you thought about being dead or what it would be like to be dead? Have you wished you were dead or wished you could go to sleep and never wake up? Do you ever wish you weren't alive anymore? If yes, describe:	Yes	No	Yes	No
2. Non-Specific Active Suicidal Thoughts General, non-specific thoughts of wanting to end one's life/commit suicide (e.g., "T've thought about killing myself") without thoughts of ways to kill oneself/associated methods, intent, or plan during the assessment period. Have you thought about doing something to make yourself not alive anymore? Have you had any thoughts about killing yourself? If yes, describe:	Yes	No	Yes	No

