12.6.2 C-SSRS, Since Last Visit

COLUMBIA-SUICIDE SEVERITY RATING SCALE (C-SSRS)

Since Last Visit - Clinical

Version 1/14/09

Posner, K.; Brent, D.; Lucas, C.; Gould, M.; Stanley, B.; Brown, G.; Fisher, P.; Zelazny, J.; Burke, A.; Oquendo, M.; Mann, J.

Disclaimer:

This scale is intended to be used by individuals who have received training in its administration. The questions contained in the Columbia-Suicide Severity Rating Scale are suggested probes. Ultimately, the determination of the presence of suicidal ideation or behavior depends on the judgment of the individual administering the scale.

Definitions of behavioral suicidal events in this scale are based on those used in **The Columbia Suicide History Form**, developed by [name] and [name], Conte Center for the Neuroscience of Mental Disorders (CCNMD), New York State Psychiatric Institute, [name]. (Oquendo M. A., Halberstam B. & Mann J. J., Risk factors for suicidal behavior: utility and limitations of research instruments. In M.B. First [Ed.] Standardized Evaluation in Clinical Practice, pp. 103-130, 2003.)

For reprints of the C-SSRS contact [name]., New York State Psychiatric Institute, [name]; inquiries and training requirements contact [contact]

© 2008 The Research Foundation for Mental Hygiene, Inc.

SUICIDAL IDEATION			
	Suicidal Behavior" section. If the answer to question 2 is "yes", or 2 is "yes", complete "Intensity of Ideation" section below.		Last sit
1. Wish to be Dead			
Subject endorses thoughts about a wish to be dead or not alive anymore,		¥7	NT-
Have you wished you were dead or wished you could go to sleep and n	ot wake up?	Yes	No
If yes, describe:			
2. Non-Specific Active Suicidal Thoughts			
General, non-specific thoughts of wanting to end one's life/commit suic	ide (e.g., "I've thought about killing myself") without thoughts of ways to kill		
oneself/associated methods, intent, or plan during the assessment period Have you actually had any thoughts of killing yourself?		Yes	No
Have you actually had any inoughts of killing yourself:			
If yes, describe:			
3. Active Suicidal Ideation with Any Methods (Not Plan)		Yes	No
	hod during the assessment period. This is different than a specific plan with time, but not a specific plan). Includes person who would say, "I thought about taking an		
overdose but I never made a specific plan as to when, where or how I w			

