7.6.5 Physical Examinations

Findings from the physical examinations will be listed for each system or area examined.

7.6.6 *C-SSRS*

C-SSRS outcomes will be summarized using number and percent of subjects by categories for suicidal ideation only, suicidal behavior only, and suicidality (ideation and behavior combined). The summary will be presented by treatment group.

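### Suicidality is screened with a children's C-SSRS form but followed up on a form without the children's wording, so ideation on treatment may be less readily elicited in both arms

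*Protocol*

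**What the plan says.** The first inclusion criterion (Protocol 4.1.1) reads "Male or female subjects, aged 8-12 years (inclusive) at the time of screening". Protocol 6.3.9.4 says that the C-SSRS versions for this study "are the Baseline version and the Since Last Visit version". The Baseline version is for Visit 1. Of the Since Last Visit version it says "This version will be used for the other study visits", which under Table 1 means Visits 4 and 6. The body text names no children's version of either form.

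The appendix does. Section 12.6.1 is titled "C-SSRS, Children's Baseline/Screening" and is dated 6/23/10. Section 12.6.2 is the form headed "Since Last Visit - Clinical", dated 1/14/09, with no children's label. Neither the protocol nor the SAP gives a reason for pairing the two.

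SAP 7.6.6 summarises the results by treatment group, as numbers and percentages of children with ideation, with behaviour, and with the two combined. Protocol 8.3.7 adds a test of proportions against placebo. The SAP drops it: under SAP 6.1 all analyses are descriptive because the study ended early.

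**The concern.** The sponsor chose child wording for the screening interview and then, on the printed forms, gave it up for the two interviews after dosing starts. For the second ideation item, the children's form offers "Have you thought about doing something to make yourself not alive anymore" as well as a direct question. The follow-up form offers only "Have you actually had any thoughts of killing yourself".

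A young child who does not follow the direct question, or shies away from it, has fewer ways to disclose at Visits 4 and 6 than at Visit 1. What is at stake is how complete the ideation counts are in the safety summary of a trial that gives an antipsychotic to children.

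**Working it through.** No figure in the plan needs reproducing. The check sets the two appended forms side by side and counts, by hand, the questions printed for the rater to put to the child.

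| Item | Children's Baseline/Screening (12.6.1) | Follow-up form (12.6.2) |
|---|---|---|
| Ideation 1, wish to be dead | 3 | 1 |
| Ideation 2, non-specific active thoughts | 2 | 1 |
| Ideation 3, method | 2 | 1 |
| Ideation 4, some intent | 1 | 1 |
| Ideation 5, plan and intent | 4 | 2 |
| **Ideation total** | **12** | **6** |
| Actual attempt | about 9 | about 9 |
| Interrupted attempt | 2 | 1 |
| Aborted attempt | 2 | 1 |
| Preparatory acts | 1 | 1 |
| Intensity of ideation | 1 | 5 |

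**Where the difference falls.** Both forms start with ideation items 1 and 2. If both are negative, the rater goes straight to behaviour. Items 3 to 5 are asked only after a yes to item 2, and the intensity section is completed only after a yes to item 1 or 2. Detection of ideation therefore rests on items 1 and 2, where the count is 3 + 2 = 5 prompts at screening and 1 + 1 = 2 at follow-up.

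**Wording.** The children's form repeatedly paraphrases suicide as making oneself not alive. It does so in items 2 to 5 and in the attempt, interrupted, aborted and preparatory items, and item 1 has a similar prompt. None of the questions on the follow-up form uses that paraphrase.

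**Behaviour items.** The actual-attempt prompts are about equal in number, and the follow-up form adds one on dangerous acts. The interrupted, aborted and preparatory items together go from 2 + 2 + 1 = 5 to 1 + 1 + 1 = 3. The two lost prompts both ask the child what he or she did. They clarify an answer more than they open the subject.

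**Intensity items.** These run the other way, 1 against 5. They come after ideation has been endorsed and so cannot recover a missed case. Frequency is also coded differently: four plain-language levels at screening, five weekly or daily rates at follow-up. Frequency codes cannot be compared between the forms.

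**The protocol's own standard for wording.** The appended MINI-KID (12.7) has separate suicidality modules for ages 6 to 8, 9 to 12 and 13 to 17, worded differently. It is given only at Visit 1 (6.5.1), so it does not cover the treatment period.

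**Size.** If the follow-up form detects a fraction r of what the children's wording would detect, counts are understated by 1 − r. The documents give no value of r, so any percentage would only restate an assumption.

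**The case against.** The strongest reply is that counting prompts does not measure detection. Both forms carry a disclaimer that the questions are suggested probes and that the person giving the scale decides. Protocol 6.3.9.4 describes a semi-structured interview. The five ideation headings match, and the definition under follow-up item 1 still includes not being alive any more, so a trained rater has the idea on the page. This stands as mitigation. It leaves the child wording to each rater in a multi-center study, and it does not explain why the wording was printed for one visit and left out for the others.

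The mismatch may also be a slip in attaching the form, since 6.3.9.4 names only a Since Last Visit version. That is possible. The appendix would then need correcting.

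A reader might infer three stronger things that the documents do not support.

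- **That the mismatch favours SPN-810.** Both blinded arms get the same form at the same visits, and SAP 7.6.6 summarises by arm with no change from baseline. A before-and-after reading would be weak anyway, because the screening form covers lifetime and the past 6 months for ideation and the follow-up form only the time since the last visit.
- **That the C-SSRS is the only suicidality monitoring.** Adverse events are sought by questioning at each visit (6.3.1.2). The parent-rated R-MOAS at Visits 4 and 6 has items on self-harm and trying to kill oneself (12.2). Neither is a structured inquiry into ideation.
- **That the follow-up form is thinner throughout.** It is not, as the actual-attempt and intensity rows show.

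**Conclusion.** The mismatch is real on the printed documents. Children aged 8 to 12 are screened in children's wording and followed up without it, with 2 prompts in place of 5 on the two items that decide whether ideation is found. The C-SSRS is the only structured instrument for ideation after dosing starts, so ideation may be less readily elicited at Visits 4 and 6, in both arms alike.

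That it would be less readily elicited is an inference from the wording. It assumes that raters stay close to the printed prompts and that child-level paraphrases help this age group to disclose. The documents do not show that the follow-up form misses cases. The consequence is limited: about 30 children were planned, those with active suicidal thoughts in the 6 months before screening are excluded (4.1.2), and the summary is descriptive. This is a minor point, worth acting on because the remedy is nearly free.

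**What to change.** Either replace Appendix 12.6.2 with a follow-up form in children's wording, or keep the form and add the children's prompts from 12.6.1 to the matching follow-up items at Visits 4 and 6. The second option needs nothing beyond what the protocol already contains. Name the chosen version in 6.3.9.4.

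The cost is one form change, processed under Protocol 9.2, and a re-briefing of raters. Visits, raters and the planned summary stay as they are.

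The SAP records early termination, so a form change may come too late for the enrolled children. In that case the report should state which form was used at Visits 4 and 6. If it was the printed one, the report should add that the on-treatment ideation counts come from fewer and less child-specific prompts than those at screening. If a children's follow-up form was used in practice, correct the appendix.

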12.7 Mini International Neuropsychiatric Interview for Children and Adolescents (MINI-KID)

M.I.N.I. KID

MINI INTERNATIONAL NEUROPSYCHIATRIC INTERVIEW FOR CHILDREN AND ADOLESCENTS

English Version 7.0.2

For

DSM-5

© Copyright 1998-2016 Sheehan DV

All rights reserved. No part of this document may be reproduced or transmitted in any form, or by any means, electronic or mechanical, including photocopying, or by any information storage or retrieval system, without permission in writing from [name]. Individual researchers, clinicians and students working in nonprofit or publicly owned settings (including universities, nonprofit hospitals, and government institutions) may make paper copies of a M.I.N.I. instrument for their **personal** clinical and research use, but **not** for institutional use, or for any financial profit or gain. Any use involving financial gain requires a license agreement from the copyright holder and payment of a per use license fee.

DISCLAIMER

Our aim is to assist in the assessment and tracking of patients with greater efficiency and accuracy. Before action is taken on any data collected and processed by this program, it should be reviewed and interpreted by a licensed clinician.

This program is not designed or intended to be used in the place of a full medical and psychiatric evaluation by a qualified licensed physician – psychiatrist. It is intended only as a tool to facilitate accurate data collection and processing of symptoms elicited by trained personnel. It is not a diagnostic test.

M.I.N.I. Xid 7.0.2 for Children and Adolescents (August 8, 2016) (8/8/16)

	Date of Birth:	Fatient Nur		an'	
	Interviewer's Name:	Time Interv	-		
	Date of Interview:	Total Time:			
	MODULES	TIME FRAME	MEETS CRITERIA	ICD-10-CM	PRIMARY DIAGNOSIS
Α	MAJOR DEPRESSIVE EPISODE	Current (2 weeks) Past Recurrent			
	MAJOR DEPRESSIVE DISORDER	Current (2 weeks) Past Recurrent		F32.x F32.x F33.x	
В	SUICIDALITY	Current (Past Month) Lifetime attempt		□ Low □ Moderate □ H	igh 🗆
	SUICIDE BEHAVIOR DISORDER	Current In early remission		(In Past Year) (1 - 2 Years Ago)	
С	MANIC EPISODE	Current Past			
	HYPOMANIC EPISODE	Current Past		☐ Not Explored	
	BIPOLAR I DISORDER	Current Past		F31.0 - F31.76 F31.0 - F31.76	
	BIPOLAR II DISORDER	Current Past		F31.81 F31.81	
	OTHER SPECIFIED BIPOLAR AND RELATED DISORDER	Current Past		F31.89 F31.89	
D	PANIC DISORDER	Current (Past Month) Lifetime		F41.0 F40.0	
Ε	AGORAPHOBIA	Current		F40.00	
F	SEPARATION ANXIETY DISORDER	Current (Past Month)		F93.0	
G	SOCIAL ANXIETY DISORDER (Social Phobia)	Current (Past Month)		F40.10	
Н	SPECIFIC PHOBIA	Current (Past Month)		F40.218 - F40.298	
I	OBSESSIVE-COMPULSIVE DISORDER	Current (Past Month)		F42.2	
J	POSTTRAUMATIC STRESS DISORDER	Current (Past Month)		F43.10	
K	ALCOHOL USE DISORDER	Past 12 Months		F10.10 - F10.21	
L	SUBSTANCE USE DISORDER (Non-alcohol)	Past 12 Months		F11.10 - F19.21	

М	TOURETTI	e's disorder	Current		F95.2	
	PERSISTEN	NT (CHRONIC) MOTOR TIC DISORDER	Current		F95.1	
	PERSISTEN	NT (CHRONIC) VOCAL TIC DISORDER	Current		F95.1	
	PROVISIO	NAL TIC DISORDER	Current		F95.0	
N	ADHD	COMBINED PRESENTATION	Past 6 Months		F90.2	
	ADHD	PREDOMINANTLY INATTENTIVE PRESENTATION	Past 6 Months		F90.0	
	ADHD	PREDOMINANTLY HYPERACTIVE TYPE PRESENTATION	Past 6 Months		F90.1	
О	CONDUCT	DISORDER	Past 12 Months		F91.1/F91.2/F91.9	
Р	OPPOSITION	ONAL DEFIANT DISORDER	Past 6 Months		F91.3	
Q	ANY PSYC	HOTIC DISORDER	Current Lifetime		F20.xx-F29 F20.xx-F29	
	MAJOR DI	EPRESSIVE DISORDER WITH PSYCHOTIC FEATURES	Current Past		F32.3/F33.3 F32.3/F33.3	
	BIPOLAR I	DISORDER WITH PSYCHOTIC FEATURES	Current Past		F31.2/F31.5/F31.64 F31.2/F31.5/F31.64	
R	ANOREXIA	A NERVOSA	Current (Past 3 Months)		F50.01/F50.02	
S	BULIMIA I	NERVOSA	Current (Past 3 Months)		F50.2	
Т	BINGE-EA	TING DISORDER	Current (Past 3 Months)		F50.81	
U	GENERALI	ZED ANXIETY DISORDER	Current (Past 6 Months)		F41.1	
٧	ADJUSTM	ENT DISORDERS	Current		F43.20 – 43.25	
w	MEDICAL,	ORGANIC, DRUG CAUSE RULED OUT			No □ Yes □ Uncerta	ain
х	AUTISM S	PECTRUM DISORDER	Cannot be ruled out		F84.0	
		THE PRIMARY DIAGNOSIS BY CHECKING THE APPROPROPERTY THE APPROPROPROPERTY THE APPROPROPERTY THE APPROPR		atural his	story?)	

INTERVIEWER INSTRUCTIONS

INTRODUCING THE INTERVIEW

The nature and purpose of the interview should be explained to the child or adolescent prior to the interview. A sample introduction is provided below:

"I'm going to ask you a lot of questions about yourself. This is so that I can get to know more about you and figure out how to help you. Most of the questions can be answered either 'yes' or 'no'. If you don't understand a word or a question, ask me, and I'll explain it. If you are not sure how to answer a question, don't guess - just tell me you are not sure. Some of the questions may seem weird to you, but try to answer them anyway. It is important that you answer the questions as honestly as you can so that I can help you. Do you have any questions before we start?"

For children under 13, we recommend interviewing the parent and the child together. Questions should be directed to the child, but the parent should be encouraged to interject if s/he feels that the child's answers are unclear or inaccurate. The interviewer makes the final decision based on his/her best clinical judgment, whether the child's answers meet the diagnostic criterion in question. With children you will need to use more examples than with adolescents and adults.

GENERAL FORMAT:

The MINI is divided into **modules** identified by letters, each corresponding to a diagnostic category.

- At the beginning of each diagnostic module (except for psychotic disorders module), screening question(s) corresponding to the main criteria of the disorder are presented in a gray box.
- At the end of each module, diagnostic box(es) permit the clinician to indicate whether diagnostic criteria are met.

CONVENTIONS:

Sentences written in «normal font» should be read exactly as written to the patient in order to standardize the assessment of diagnostic criteria.

Sentences written in «CAPITALS» should not be read to the patient. They are instructions for the interviewer to assist in the scoring of the diagnostic algorithms.

Sentences written in **«bold»** indicate the time frame being investigated. The interviewer should read them as often as necessary. Only symptoms occurring during the time frame indicated should be considered in scoring the responses.

Answers with an arrow above them (➡) indicate that one of the criteria necessary for the diagnosis or the diagnoses is not met. In this case, the interviewer should go to the end of the module and circle «NO» in all the diagnostic boxes and move to the next module.

When terms are separated by a slash (/) the interviewer should read only those symptoms known to be present in the patient (for example, question L2b).

Phrases in (parentheses) are clinical examples of the symptom. These may be read to the patient to clarify the question.

FORMAT OF THE INTERVIEW

The interview questions are designed to elicit specific diagnostic criteria. The questions should be read verbatim. If the child or adolescent does not understand a particular word or concept, you may explain what it means or give examples that capture its essence. If a child or adolescent is unsure if s/he has a particular symptom, you may ask him/her provide an explanation or example to determine if it matches the criterion being investigated. If an interview item has more than 1 question, the interviewer should pause between questions to allow the child or adolescent time to respond.

Questions about the duration of symptoms are included for diagnoses when the time frame of symptoms is a critical element. Because children may have difficulty estimating time, you may assist them by helping them connect times to

significant events in their lives. For example, the starting point for "past year" might relate to a birthday, the end or beginning of a school year, a particular holiday or another annual event.

RATING INSTRUCTIONS:

All questions must be rated. The rating is done at the right of each question by circling either YES or NO. Clinical judgment by the rater should be used in coding the responses. The rater should ask for examples when necessary, to ensure accurate coding. The child or adolescent should be encouraged to ask for clarification on any question that is not absolutely clear.

The clinician should take each dimension of the question into account (for example, time frame, frequency, severity, and/or alternatives).

Symptoms better accounted for by an organic cause or by the use of alcohol or drugs should not be coded positive in the MINI KID. The MINI KID has questions that investigate these issues (Module W).

For any questions, suggestions, need for a training session or information about updates of the MINI Kid, please contact: [name]., M.B.A.

University of South Florida College of Medicine

[contact]

email: [contact]

For licensing, permissions, or questions, contact: [contact]

A. MAJOR DEPRESSIVE EPISODE

(➡ MEANS: GO TO THE DIAGNOSTIC BOX, CIRCLE NO IN THE DIAGNOSTIC BOX, AND MOVE TO THE NEXT MODULE)

A1	а	At any time in your life, did you feel sad or depressed? Felt down or empty or hopeless? Felt grouchy or annoyed? Did you feel this way most of the time, for at least 2 weeks?		
		IF YES TO ANY, CONTINUE. IF NO TO ALL, CODE NO TO A1a AND A1b.	NO	YES
	b	For the past 2 weeks, did you feel this way, most of the day, nearly every day?	NO	YES
A2	а	At any time in your life, were you bored a lot or much less interested in things (like playing your favorite games)? Have you felt that you couldn't enjoy things? Did you feel this way most of the time, for at least 2 weeks?		
		IF YES TO ANY, CONTINUE. IF NO TO ALL, CODE NO TO A2a AND A2b.	NO	YES
	b	For the past 2 weeks, did you feel this way, most of the day, nearly every day?	NO	YES
		IS A1 a OR A2 a CODED YES?	→ NO	YES

A3 IF **A1b** OR **A2b** = YES: EXPLORE THE CURRENT AND THE MOST SYMPTOMATIC PAST EPISODE, OTHERWISE IF **A1b** AND **A2b** = **NO**: EXPLORE **ONLY** THE MOST SYMPTOMATIC PAST EPISODE

	In the past two weeks, when you felt depressed / grouchy / uninterested:	Past 2 \	Neeks	Past E	pisode
а	Were you less hungry or more hungry most days? Did you lose or gain weight without trying? [i.e., by \pm 5% of body weight in the past month]? IF YES TO EITHER, CODE YES.	NO	YES	NO	YES
b	Did you have trouble sleeping almost every night ("trouble sleeping" means trouble falling asleep, waking up in the middle of the night, waking up too early or sleeping too much)?	NO	YES	NO	YES
С	Did you talk or move slower than usual? Were you fidgety, restless or couldn't sit still almost every day? Did anyone notice this? IF YES TO EITHER, CODE YES.	NO	YES	NO	YES
d	Did you feel tired most of the time?	NO	YES	NO	YES
е	Did you feel bad about yourself most of the time? Did you feel guilty most of the time? IF YES TO EITHER, CODE YES.	NO	YES	NO	YES
	IF YES, ASK FOR EXAMPLES. LOOK FOR DELUSIONS OF FAILURE, OF INADEQUACY, OF RUIN OR OF OF NEEDING PUNISHMENT OR DELUSIONS OF DISEASE OR DEATH OR NIHILISTIC OR SOMATIC DELETED THE EXAMPLES ARE CONSISTENT WITH A DELUSIONAL IDEA. Current Episode No Yes Past Episode No Yes				
f	Did you have trouble concentrating or thinking or did you have trouble making up your mind almost every day? IF YES TO EITHER, CODE YES.	NO	YES	NO	YES
g	Did you feel so bad that you wished that you were dead? Did you think about hurting yourself? Did you have thoughts of death? Did you think about killing yourself? IF YES TO ANY, CODE YES. (FEAR OF DYING DOES NOT COUNT HERE).	NO	YES	NO	YES

A4	Did these sad, depressed feelings cause a lot of problems at home? At school? With friends? With other people? Or in some other important way?	2 Weeks YES	Past Epi NO	sode YES
A 5	In between your times of depression, were you free of depression or sadness for of at least 2 months?	N/A	NO	YES
	ARE 5 OR MORE ANSWERS (A1-A3) CODED YES AND IS A4 CODED YES FOR THAT TIME FRAME?	NO		YES
	AND	MAJ	OR DEPRI EPISODI	
	IS "RULE OUT ORGANIC CAUSE (W2 SUMMARY)" CODED YES?			
	SPECIFY IF THE EPISODE IS CURRENT AND / OR PAST.	CURRI PAST RECUI		
	IF A5 IS CODED YES, CODE YES FOR RECURRENT.	INECO.		
A6 a	How many episodes of depression did you have in your lifetime?			
	Between each episode there must be at least 2 months without any significant depre	ssion.		

B. SUICIDALITY (for ages 13 through 17)

				Points
	In the past month did you:			
B1	Have any accident? This includes taking too much of your medication by accident. IF NO TO B1, SKIP TO B2. IF YES, ASK B1a:	NO	YES	0
B1a	Plan or expect to hurt yourself on purpose in any accident, or put yourself in a position where you could be hurt?	NO	YES	0
	IF NO TO B1a, SKIP TO B2. IF YES, ASK B1b:			
B1b	Want to die as a result of any accident?	NO	YES	0
B2	Think that you would be better off dead or wish you were dead or need to be dead?	NO	YES	1
В3	Think about hurting yourself, with the possibility that you might die? Or did you think about killing yourself? IF YES TO EITHER, CODE YES. IF NO TO B2 + B3, SKIP TO B4. OTHERWISE ASK:	NO	YES	6
	How often? How strong were the thoughts?			
	Occasionally			
B4	Hear a voice or voices telling you to kill yourself or have a dream or a nightmare about killing yourself? IF YES, mark either or both:	NO	YES	4
B 5	Have a way or a method in mind to kill yourself (i.e. how)?	NO	YES	8
В6	Think about what you would use to kill yourself?	NO	YES	8
В7	Think about where you would go to kill yourself?	NO	YES	8
В8	Think about when you could kill yourself?	NO	YES	8
В9	Think about anything you would like to finish before trying to kill yourself? (e.g. writing a suicide note)	NO	YES	8
B10	Expect to go through with a plan to kill yourself?	NO	YES	8
	IF YES, mark either or both: did you intend to act at the time? did you intend to act at some time in the future?			
B11	Expect to die as a result of trying to hurt yourself?	NO	YES	8
	IF YES, mark either or both: did you intend to die by suicide at the time? did you intend to die by suicide at some time in the future?			
B12	Feel the need or impulse to kill yourself or to plan to kill yourself sooner rather than later?	NO	YES	8
	IF YES, mark either or both: $\ \square$ was it to kill yourself? $\ \square$ was it to plan to kill yourse	lf?		
	IF YES, mark either or both: was it for no good reason? was it for some good reaso IN ASSESSING WHETHER THIS WAS LARGELY UNPROVOKED ("FOR NO GOOD REASON") OR PROV" "5 minutes before this impulse to kill yourself, could you have predicted it would occur at that to IF NO TO B12, SKIP TO B14.	VOKED AS	SK:	

B13	Have difficulty resisting these impulses to kill yourself?		NO	YES	8
B14	Do things to prepare to kill yourself, but were interrupted or sto before harming yourself? IF NO TO B14, SKIP TO B15. OTHERWISE GO TO B14a.	opped yourself,	NO	YES	
B1 4a	Do things to get ready to kill yourself, but you did not start to ki	ill yourself?	NO	YES	9
B14b	Do things to get ready to kill yourself, but then you stopped yo you hurt yourself ("aborted")?	urself just before	NO	YES	10
B14c	Do things to get ready to kill yourself, but then someone or son stopped you just before you hurt yourself ("interrupted")?	nething	NO	YES	11
B15	Hurt yourself on purpose without trying to kill yourself? (B15 IS NOT COUNTED AS SUICIDAL BEHAVIOR)		NO	YES	0
B16	Try to kill yourself? IF NO TO B16, SKIP TO B17.		NO	YES	
B16a	Start to kill yourself, but then you decided to stop and you did not finish the attempt?		NO	YES	12
B16b	Start to kill yourself, but then someone or something stopped yand you did not finish the attempt?	you	NO	YES	13
B16c	Do everything you could to try to kill yourself completely, as you A suicide attempt means you did something where you could powith at least a slight intent to die. IF NO, SKIP TO B17.		NO	YES	14
	Hope to be rescued / survive Expected / intended to die				
B17	TIME SPENT PER DAY WITH ANY SUICIDAL IMPULSES, THOUGH Usual time spent per day: hours minutes Least amount of time spent per day: hours minutes Most amount of time spent per day: hours minutes				
	In your lifetime:				
B18	Did you ever try to kill yourself? IF YES, how many times? IF YES, when was the last suicide attempt?		NO	YES	4
	Current: within the past 12 months				
	In early remission: between 12 and 24 months ago				
	In remission: more than 24 months ago				
	"A suicide attempt is any self-injurious behavior, with at least so the individual intended to kill him-or herself, at least to some do circumstance. For example, it is defined as a suicide attempt if it could be lethal, even though denying intent." (FDA Guidance for and C-CASA definition). Posner K et al. Am J Psychiatry 2007; 16 http://www.fda.gov/Drugs/GuidanceComplianceRegulatoryInformation	egree, can be explicit or inferred f t is clearly not an accident or if th r Industry Suicidal Ideation and Bo 4 (7): 1035-1043 &	rom the e individ	behavior or ual thinks the	act
B19	How likely are you to try to kill yourself within the next 3 month ANY LIKELIHOOD > 0 % ON B19 SHOULD BE CODED YES .	is on a scale of 0-100%%	NO	YES	13
M.I.N.I.	Kid 7.0.2 (August 8, 2016) (8/8/16).				

IS AT LEAST 1 OF THE ABOVE (EXCEPT B1) CODED YES?	NO	YES
IF YES, ADD THE TOTAL POINTS FOR THE ANSWERS (B1-B19) CHECKED 'YES' AND SPECIFY THE SUICIDALITY SCORE CATEGORY AS INDICATED IN THE DIAGNOSTIC BOX:	SUICID	ALITY
INDICATE WHETHER THE SUICIDALITY IS CURRENT (PAST MONTH) OR A LIFETIME SUICIDE ATTEMPT OR BOTH BY MARKING THE APPROPRIATE BOXES OR BY LEAVING EITHER OR BOTH OF THEM UNMARKED. CURRENT = ANY POSITIVE RESPONSE IN B1a THROUGH B16c (EXCEPT B15) OR ANY TIME SPENT IN B17 .	1-8 points Lo 9-16 points M ≥ 17 points H	loderate 🗌
LIFETIME ATTEMPT = B18 CODED YES. LIKELY IN THE NEAR FUTURE = B19 CODED YES.	CURRENT	
MAKE ANY ADDITIONAL COMMENTS ABOUT YOUR ASSESSMENT OF THIS PATIENT'S CURRENT AND NEAR FUTURE SUICIDALITY IN THE SPACE BELOW:	LIFETIME ATTE	_
IS B18 CODED YES ?	NO	YES
IS B18 CODED YES? AND A YES RESPONSE TO	NO SUICIDAL E DISOR	BEHAVIOR
	SUICIDAL E	BEHAVIOR
AND A YES RESPONSE TO	SUICIDAL E	BEHAVIOR RDER

B. SUICIDALITY (for ages 9 through 12)

	In the past month did you:		P	oints
B1	Have an accident? This includes taking too much of your medication by accident.	NO	YES	0
	IF NO TO B1, SKIP TO B2. IF YES, ASK B1a:			
B1a	Plan or expect to hurt yourself on purpose in an accident?	NO	YES	0
	IF NO TO B1a, SKIP TO B2. IF YES, ASK B1b:			
B1b	Try to die as a result of an accident?	NO	YES	0
B2	Think (even momentarily) that you would be better off dead or wish you were dead?	NO	YES	1
В3	Think about hurting yourself, with the possibility that you might die? Or did you think about killing yourself? IF YES TO EITHER, CODE YES. IF NO TO B2 + B3, SKIP TO B4. OTHERWISE ASK:	NO	YES	6
	How often? How strong were the thoughts?			
	Occasionally			
B4	Hear a voice or voices telling you to kill yourself or have a dream or a nightmare	NO	YES	4
	about killing yourself? IF YES, mark either or both: was it a voice or voices? was it a dream or a nightmare?			
B 5	Think about how to kill yourself?	NO	YES	8
B6	Think about what you would use to kill yourself?	NO	YES	8
В7	Think about where you would go to kill yourself?	NO	YES	8
В8	Think about when to kill yourself?	NO	YES	8
В9	Think about anything you would like to finish before you tried to kill yourself? (e.g. writing a suicide note)	NO	YES	8
B10	Want to go through with a plan to kill yourself?	NO	YES	8
B11	Want to die by hurting yourself?	NO	YES	8
B12	Think all of a sudden about killing yourself sooner rather than later? IF YES, mark either or both: was this to kill yourself? was this to plan to kill yourself?	NO self?	YES	8
	IF YES, mark either or both: was it for no good reason? was it for some good reason in ASSESSING WHETHER THIS WAS LARGELY UNPROVOKED ("FOR NO GOOD REASON") OR PROV "5 minutes before this impulse to kill yourself, could you have predicted it would occur at that the NO TO B12, SKIP TO B14.	OKED AS	K:	
B13	Have difficulty resisting (or fighting against) these impulses to kill yourself?	NO	YES	8
B14	Do things to prepare to kill yourself?	NO	YES	

B1 4a	Do things to get ready to kill yourself, but you did not start to kill yourself?	NO	YES	9
B14b	Do things to get ready to kill yourself, but then you stopped yourself just before you hurt yourself ("aborted")?	NO	YES	10
B1 4c	Do things to get ready to kill yourself, but then someone or something stopped you just before you hurt yourself ("interrupted")?	NO	YES	11
B1 5	Hurt yourself on purpose without trying to kill yourself? (B15 IS NOT COUNTED AS SUICIDAL BEHAVIOR)	NO	YES	0
B16	Try to kill yourself? IF NO TO B16, SKIP TO B17.	NO	YES	
B1 6a	Start to kill yourself, but then you decided to stop and did not finish trying?	NO	YES	12
B16b	Start to kill yourself, but then someone or something stopped you and did not finish the attempt?	NO	YES	13
B16c	Do everything you could to try to kill yourself? A suicide attempt means you did something where you could possibly be injured, with at least a slight intent to die. IF NO , SKIP TO B17 .	NO	YES	14
	Hope to be rescued / survive Expected / intended to die			
B17	TIME SPENT PER DAY WITH ANY SUICIDAL IMPULSES, THOUGHTS OR ACTIONS: Usual time spent per day: hours minutes. Least amount of time spent per day: hours minutes. Most amount of time spent per day: hours minutes.			
	In your lifetime:			
B18	Did you ever try to kill yourself? IF YES, how many times? IF YES, when was the last suicide attempt? Current: within the past 12 months In early remission: between 12 and 24 months ago In remission: more than 24 months ago	NO	YES	4
	"A suicide attempt is any self-injurious behavior, with at least some intent (> 0) to die as a rethe individual intended to kill him-or herself, at least to some degree, can be explicit or infecircumstance. For example, it is defined as a suicide attempt if it is clearly not an accident of could be lethal, even though denying intent." (FDA Guidance for Industry Suicidal Ideation and C-CASA definition). Posner K et al. Am J Psychiatry 2007; 164 (7): 1035-1043 & http://www.fda.gov/Drugs/GuidanceComplianceRegulatoryInformation/Guidances/default.htm/	rred from the r if the indivi	e behavior dual think	or s the act
B1 9	How likely are you to try to kill yourself within the next 3 months on a scale of 0-100% ANY LIKELIHOOD > 0% ON B19 SHOULD BE CODED YES.	% NO	YES	13

IS AT LEAST 1 OF THE ABOVE (EXCEPT B1) CODED YES?	NO	YES
IF YES, ADD THE TOTAL POINTS FOR THE ANSWERS (B1-B19) CHECKED 'YES' AND SPECIFY THE SUICIDALITY SCORE CATEGORY AS INDICATED IN THE DIAGNOSTIC BOX:	SUICID	PALITY
INDICATE WHETHER THE SUICIDALITY IS CURRENT (PAST MONTH) OR A LIFETIME SUICIDE ATTEMPT OR BOTH BY MARKING THE APPROPRIATE BOXES OR BY LEAVING EITHER OR BOTH OF THEM UNMARKED. CURRENT = ANY POSITIVE RESPONSE IN B1a THROUGH B16c (EXCEPT B15) OR ANY TIME SPENT IN B17 .	1-8 points L 9-16 points N ≥17 points H	Moderate 🗆
LIFETIME ATTEMPT = B18 CODED YES. LIKELY IN THE NEAR FUTURE = B19 CODED YES.	CURRENT	
MAKE ANY ADDITIONAL COMMENTS ABOUT YOUR ASSESSMENT OF THIS PATIENT'S CURRENT AND NEAR FUTURE SUICIDALITY IN THE SPACE BELOW:	LIFETIME ATTE	
IS B18 CODED YES?	NO	YES
IS B18 CODED YES? AND A YES RESPONSE TO	NO SUICIDAL E DISOI	BEHAVIOR
	SUICIDAL E	BEHAVIOR
AND A YES RESPONSE TO	SUICIDAL E	BEHAVIOR RDER

B. SUICIDALITY (for ages 6 through 8)

	In the past month did you:		F	Points
B1	Have an accident? This includes taking too much of your medication by accident. IF NO TO B1, SKIP TO B2. IF YES, ASK B1a:	NO	YES	0
